3.4.3. Sample size calculation

We conducted a power analysis (in June 2014) to assess ability to detect intervention effects on selected outcomes. At the time, we found that the indicators would provide sufficient power, between 65% and 99%, depending on the indicator – please see Doyle et. al (2018) for additional detail. While we do expect greater attrition than in previous rounds, we had very high response rates and low attrition in the study thus far. At most recent data collection with the full sample, 21-months post-baseline, 94% of the men and 97% of the women were surveyed.

It is difficult to estimate effect sizes on children's outcomes in the context of a couples intervention rather than a targeted early childhood development intervention, and with limited data available. To determine the appropriate sample size for the child assessments, we consulted several experts through the Saving Brains Grand Challenges platform, who based on their expertise with the assessment tools and randomized trials of early childhood development programs, recommended a minimum sample size of 300-400 children per arm.

3.4.4 Sample selection

The primary sampling unit, and unit of analysis, is the individual respondent within the household. All men enrolled in the original Bandebereho RCT who are known to still be alive at the 21-month

follow-up (n=1,193) will be assessed for eligibility in the current study and included in the sample, as well as their current female partners.

For the six-year follow-up, we will be randomly selecting 800 households with children ages 4-7 for observational assessments of a selected child. The children will be selected randomly from a list of families with eligible children, stratified by intervention and control group status, as well as by district. Only one child per family would be eligible for assessment. If the family has more than one child ages 4-7, the child closest to age 6 would be selected. If more than one child fits that criterion (e.g. one child age 5 and another child age 7), the youngest child is selected. If the family has twins ages 4-7, one child is randomly selected.

Sampling will be done by Laterite, an external data collection firm.

4. Research instruments, outcome measurement and analysis plans

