1.2 Previous evaluation findings

A randomized controlled trial (RCT) of the Bandebereho intervention was previously conducted with 1,199 couples (575 treatment; 624 control) and demonstrated significant impacts on a range of gender and health-related outcomes. As reported in PLOS One^{iii} , at 21-months after the baseline (16 months post-intervention), compared to a control group, participating families reported: less past-year physical (OR 0.37, p<0.001) and sexual intimate partner violence (IPV) (OR 0.34, p<0.001), and less physical punishment of children (women: OR 0.56, p = 0.001; men: OR 0.66, p = 0.005). Women in the intervention reported greater antenatal care (ANC) attendance (IRR 1.09, p<0.001) and male accompaniment to ANC (IRR 1.50, p<0.001), as well as modern contraceptive use (OR 1.53, p = 0.004), compared to women in the control group. Additionally, women in the intervention group reported higher levels of men's participation in childcare and household tasks (women: beta 0.39, p<0.001; men: beta 0.33, p<0.001) and less dominance of men in a series of household decisions. Forthcoming analyses also indicate that compared to the control group, the intervention group reported: lower rates of maternal depression, lower rates of men's alcohol consumption, and greater time spent by parents in stimulating interaction with their children.

The results of the Bandebereho RCT have contributed to critical evidence gaps on the impact of male engagement approaches. While several trials from the Global South had previously shown positive impacts on outcomes related to intimate partner violence (IPV),^{iv,v,vi,vii,viii} family planning,^{ix,x} and maternal health,^{xi,xii,xiii} rigorous evidence of effectiveness of male engagement approaches has remained limited.^{xiv,xv,xvi} In addition, few studies have evaluated interventions addressing multiple outcomes and even fewer have examined impact on household gender and power dynamics^{xvii,xviii} in the way that the Bandebereho RCT has done. While the Bandebereho RCT collected data over a longer timeframe than many studies (at 16 months post-intervention), it does not provide an understanding of the longer-term impacts of the intervention.

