3.4 Sampling

3.4.1. Sampling frame

The sampling frame for this study includes all participants from among the 1,199 couples (576 treatment; 624 control) who enrolled in the original RCT study in 2015, who are living, traceable, and remain eligible for the study. We will also conduct child assessments with a randomly selected subsample of 800 of their children born around or shortly after the intervention, aged between 4 and 7 years (400 treatment; 400 control).

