4.2. Proposed analysis

Proposed analyses include generating descriptive statistics on all variables, as well as examining differences between the intervention and control group participants on primary outcomes using t-test, chi2-tests, and generalized estimating equations with robust standard errors to account for clustering by facilitator.

5. Field work plans

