5.3 Scheduling appointments

For couples with separate contact information for each partner, enumerators will contact all male RCT participants who agreed to the follow up to inform them of the date, time, and location of the men's interview. Enumerators will then contact the female partners separately to inform them of the date, time, and location of the women's interview. If the family is selected for a child interview, both partners will also be informed of the date, time, and location for the child assessment and will be asked to bring a copy of their child's vaccination card to the interview to confirm the child's date of birth.

For couples with only one phone number, the enumerator will call and ask to speak to each partner individually to provide the interview information. If one partner is not available, the enumerator will ask the partner with whom they speak to relay the information to their partner.

On the day of the survey, informed consent will be obtained from each respondent according to the procedures described in section 6.2.

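### The comparisons named for the child outcomes carry no age term, although the children span ages 4 to 7 and exact date of birth is already confirmed

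*Protocol*

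**What the plan says.** - **Outcomes.** Table 4.1 lists child development among the primary outcomes: the parent-reported Strengths and Difficulties Questionnaire (SDQ) and, pending piloting, the directly administered IDELA. These serve objective (b). The table does not say how either is scored.
- **Ages and numbers.** Sections 3.4.1 and 3.4.4 call for 800 children aged 4 to 7, 400 per arm.
- **Selection.** Children are "selected randomly from a list of families with eligible children, stratified by intervention and control group status, as well as by district" (3.4.4). Within a family, "If the family has more than one child ages 4-7, the child closest to age 6 would be selected".
- **Analysis.** Section 4.2 proposes to compare the arms on primary outcomes "using t-test, chi2-tests, and generalized estimating equations with robust standard errors to account for clustering by facilitator". It names no covariate.
- **Age data.** Parents are asked "to bring a copy of their child's vaccination card to the interview to confirm the child's date of birth" (5.3). Section 5.9 says that photographs of the cards serve data quality monitoring and are destroyed after review. No role in scoring or analysis is stated for the date of birth.
- **Contraception.** Section 1.2 reports higher modern contraceptive use in the intervention arm at 21 months, OR 1.53.

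**The concern.** Scores on a direct learning assessment can be expected to rise with age between 4 and 7. The case is strongest for IDELA; for the SDQ, a parent report of problems and prosocial behaviour, no comparable slope is argued here. A comparison without age treats this growth as noise.

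The child sample has little precision to give away. Section 3.4.3 bases it on expert advice for a minimum of 300 to 400 per arm and says that the effect size is hard to estimate. Leaving age out could hide a modest effect that the same children would show with age in the model.

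A second, weaker worry is bias. If the intervention changed when later children were born, the arms could differ in mean age at assessment, and scores that rise with age would carry that difference into the result.

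**Working it through.** **The plan's own figure.** The 300 to 400 per arm cannot be reproduced, because no effect, SD, alpha or power is given for child outcomes. For orientation, with two-sided alpha 0.05 and 80% power (both assumed), the detectable effect is (1.960 + 0.842) × √(2/n): 0.229 SD at 300 per arm and 0.198 SD at 400. An effect of 0.20 SD needs 393 per arm.

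**Assumptions.** R² is the share of score variance explained by age, taken as 0.10 to 0.50. Age is uniform over 4 to under 8 years (SD 4/√12 = 1.155 years) or over 4.0 to 7.0 (SD 3/√12 = 0.866 years). Facilitator clustering is ignored. With SD 1.155, an R² of 0.10, 0.25 or 0.50 corresponds to a slope of √(R²/(1 − R²))/1.155 = 0.29, 0.50 or 0.87 within-age SD per year.

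**Step 1: precision.** Adjustment reduces the residual SD to √(1 − R²). The unadjusted comparison is then worth 800 × (1 − R²) age-adjusted children. Power at 400 per arm and 0.20 SD is Φ(0.20 × √200/√(1 − R²) − 1.96).

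| R² | 800 unadjusted children are worth | Power with age | Detectable effect with age |
|---|---|---|---|
| 0 (age left out) | – | 80.7% | 0.198 SD |
| 0.10 | 720 | 84.6% | 0.188 SD |
| 0.25 | 600 | 90.4% | 0.172 SD |
| 0.50 | 400 | 97.9% | 0.140 SD |

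**Step 2: chance imbalance.** With age SD 1.155, the arm difference in mean age has standard error 1.155 × √(2/400) = 0.082 year. The unadjusted test already carries this in its standard error. In 20,000 simulated trials per setting, its type I error was 4.9% at R² 0.25 and 5.1% at R² 0.50.

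**Step 3: systematic imbalance.** The bias is √R² × (difference in mean age)/(age SD). For R² 0.10, 0.25 and 0.50:

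- 0.1 year, age SD 1.155: bias 0.03, 0.04, 0.06 SD; type I error 7%, 9%, 14%.
- 0.2 year, age SD 1.155: bias 0.05, 0.09, 0.12 SD; type I error 12%, 23%, 41%.
- 0.1 year, age SD 0.866: bias 0.04, 0.06, 0.08 SD; type I error 8%, 13%, 21%.

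**Step 4: could such a gap arise?** Randomisation followed the February/March 2015 baseline, and assessment is planned for April/May 2021 (3.2). Children conceived after randomisation were born from about December 2015, so they are at most about 5.4 years old and are the youngest eligible. On the four-year reading they make up 1.4/4 = 35% of the window, with mean age 4.7, against 6.7 for the rest. If the intervention arm had 20% fewer of them (assumed), its mean age would be (0.35 × 0.8 × 4.7 + 0.65 × 6.7)/(0.28 + 0.65) = 6.10, against 6.00: a gap of about 0.1 year. Halving them gives (0.175 × 4.7 + 0.65 × 6.7)/0.825 = 6.28, a gap of about 0.28 year. The closest-to-6 rule, ignored here, would weaken the effect.

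**The case against.** The strongest reply is that covariates and score derivation are commonly left to a statistical analysis plan, which is not shown. Section 4.2 presents its methods as proposals; GEE accepts covariates; and the note under Table 4.1 mentions another variable, participation in later programmes, that 4.2 does not repeat. So 4.2 is not a complete model specification. This stands as far as it goes. What remains is that a t-test, which takes no covariate, is named for primary outcomes, and a better comparison is available from data already collected.

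Three stronger readings are tempting, and the document does not support them:

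- **Raw scores will be compared and age ignored.** The Protocol says neither. This would be an inference from silence.
- **The sample is unbalanced on age.** Men were randomised and households are drawn at random within arm and district, so age is balanced in expectation apart from any effect on births. The closest-to-6 rule also narrows the spread in families with several eligible children.
- **Growth will pass for an intervention effect.** This needs a systematic age gap. The contraception result makes one possible, but no births by arm are given. A later birth also does not displace a sibling aged 6.

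It is also fair that the R² values are assumptions and that the argument is weaker for the SDQ.

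**Conclusion.** The point holds as an improvement to a stated comparison. The firm part is precision: leaving age out costs the equivalent of 10% to 50% of the 800 children, if age explains 10% to 50% of score variance. At 0.20 SD and 400 per arm, that is about 81% power instead of 85% to 98%. The effect, alpha and R² are assumptions, and clustering is left out.

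Bias is secondary. Chance imbalance leaves type I error at 5%. A systematic gap of about 0.1 year would raise it to between 7% and 21% over the assumptions shown, but the document gives no basis for fixing the gap. Nothing here shows that the planned child result would be biased.

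**What to change.** In section 4.2, name the primary child comparison as a GEE or regression adjusted for age in months at assessment (continuous, in a flexible form such as a spline) and sex, or as a comparison of internally age-standardised scores, in place of the unadjusted t-test. If this is already specified elsewhere, point to it. Keep date of birth as an analysis field after the card photographs are destroyed, with the parent-reported date where there is no card. Report age at assessment by arm.

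No age-band sampling stratum is needed. With age in the model it adds little, and a draw proportional to age within each arm would reproduce an arm difference in age. Adjustment deals with the part of any arm difference that works through age; it does not correct other differences in which families have an eligible child.

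The cost is a few lines of wording and no new measurement. The one drawback is less exact ages for children without a card.

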4.1 Research instruments and indicators

The outcomes assessed via men's and women's responses will be collected through a survey questionnaire, administered in-person by a team of sex-matched enumerators trained in survey administration and research ethics. Child outcomes will be assessed through standard structured observation and assessment tools previously used in Rwanda, by trained and experienced enumerators from Laterite. Children will be accompanied by a trusted adult (typically a parent), and for safety considerations and the comfort of both the child and the parent, will never be alone with the enumerator.

The research instruments will collect data on outcome measures related to five domains:

- **Reproductive, maternal, and newborn health (RMNH) and men's engagement**: women's attendance of antenatal care (ANC) visits; men's accompaniment and/or participation in ANC; and modern contraceptive use.
- Gender attitudes and household dynamics: attitudes about gender norms; men's participation in caregiving and domestic tasks; household division of labor and time spent on household tasks; men's dominance of household decision-making; couple communication; relationship dynamics and quarreling.
- Intimate partner violence, risk behaviors, and men's and women's health and well-being: intimate partner violence; attitudes about violence against women; men's alcohol use; stress, support, and mental health.

- **Parenting and parental self-efficacy**: couple division of childcare; time spent on childcare tasks; positive parenting behaviors such as stimulation, responsiveness, and positive discipline; use of violence and/or harsh discipline against children; attitudes about violence against children; feelings of parental self-efficacy.
- **Child development**: measures of social and emotional skills including prosocial behavior, conduct problems and peer relationships; executive functioning; emergent numeracy; and height and weight.

Data on children's outcomes will be collected from parent reports as well as through direct child observation and collection of anthropometric data. Child observations will be conducted with a sample of 800 children ages 4-7 (who would have been born in the period during or directly after the intervention). Table 4.1 presents the primary outcomes of interest and how they will be measured.

Primary	Outcome	Respondents	Instrument, Indicators
Outcomes			
Reproductive and maternal health behaviors	Women's antenatal care (ANC) attendance Men's	Women Women; Men	Women will be asked how many ANC visits they attended during their current pregnancy (if applicable) and during their most recent pregnancy. Women will be asked how many times their
	accompanimen t to ANC		partner accompanied them to ANC visits; men will be asked how many times they accompanied their partner.
	Modern contraceptive use	Women; Men	Women and men will be asked about their or their partner's current use of any modern contraceptive method (e.g., implant, injection, male or female condom, pill, IUD, vasectomy, hysterectomy).
Experiences of intimate partner violence	Women's past year experience of intimate partner violence	Women	Women will be asked items adapted from the WHO multi-country study ^{xxi} , regarding how many times in the past 12 months their partner had: 1) slapped them or threw something at them that could hurt them; 2) pushed or shoved them; 3) hit them with a fist or with something else that could hurt them; 4) kicked, dragged, beat, choked or burned them; 5) threatened to use or actually used a knife or stick against them. Response options will include O=never, 1=once, 2=a few times, and 3=frequently.

Table 4.1. Primary outcomes and Indicators

			Women will be asked how many times in the past 12 months: 1) their partner had forced them to have sex when they did not want to; and 2) they had consented to sex out of fear of what their partner might do if they refused. Response options will include O=never, 1=once, 2=a few times, and 3=frequently.
Parenting behaviors	Physical punishment of children	Women; Men	Men and women will be asked items adapted from the Multiple Indicator Cluster Survey (MICS) child discipline module, ^{xxii} including whether or not they: 1) shook the child; 2) spanked, slapped or hit the child on the bottom with a bare hand; 3) hit the child on the bottom or elsewhere on the body with something like a belt, stick or other hard object; 4) hit or slapped the child on the face, head, or ears; 5) hit or slapped the child on the hand, arm, or legs; 6) beat the child up, meaning hit the child over and over as hard as one could; and 7) made the child kneel on the ground for a period of time. Response options will include O=no, 1=yes.
	Parental stimulation, responsiveness and warmth	Women; Men	Parental warmth, responsiveness, and positive discipline behaviors will be assessed through the MICS early childhood module, and potentially the HOME or IDELA observation or parent questionnaire. These include questions on parental behaviors such as teaching the child something, playing with the child, praising the child, etc.
Child development	Social and emotional development	Women, men reporting on index child	Parents will complete the Strengths and Difficulties questionnaire, which includes 25 items on children's internalizing problems, externalizing problems, and prosocial behaviors.
	Cognitive development and executive functioning	Child assessment	Pending piloting, cognitive development, executive functioning, and social and emotional skills will be assessed by trained interviewers administering the International

			Development and Early Learning Assessment (IDELA), which has previously been used in Rwanda.
Gendered division of childcare and household tasks	Division of childcare and household tasks	Women; Men	Men and women will be asked how they divided a series of childcare and household tasks with their partner. Response options will be woman always does the task, task is shared equally or done together, man always does the task, someone else does it, or not applicable.
	Time spent on childcare, household tasks, and paid work	Women; Men	Respondents will be asked on how many days in the previous week they did each of a series of childcare, household tasks, and activities related to paid work, and how much time (in hours or fractions of hours) on average they spent on the task on each of those days.
Men's dominance in household decision- making	Men having the final say on key household decisions	Women; Men	Men and women will be asked who has the final say in making a series of family-related decisions. Response options will be self; partner; both have the same say; someone else; don't know.

Note that the six-year follow up findings may be confounded by subsequent participation of couples from the control group in the Bandebereho scale-up in Musanze district in 2020, and a similar program implemented under Rwamrec in Karongi district. Participants from these districts will be asked about their participation in these programs, and the results will be included in the analysis as appropriate.

We request permission to make minor changes to the tools based on pre-testing prior to data collection. Changes may include deletion of some items or rewording of items for clarity and relevance. No new domains and no entirely new instruments will be used without prior approval.

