1.1. Description of the intervention being evaluated

The Bandebereho couples' intervention being assessed was concluded in 2015. The intervention engaged men and their partners in participatory, small group sessions of critical reflection and dialogue. The intervention used a structured curriculum which was approved by the Rwanda Ministry of Health/Rwanda Biomedical Center. Men participating in the Bandebereho intervention were invited to 15 sessions (maximum 45 hours) and their partners to 8 (maximum 24 hours). Sessions addressed: gender and power; fatherhood; couple communication and decision-making; intimate partner violence; caregiving; child development; and male engagement in reproductive and maternal health.

The intervention creates a structured space for men and women to:

- question and critically reflect on gender norms and how these shape their lives;
- rehearse equitable and non-violent attitudes and behaviors in a comfortable space with supportive peers; and
- internalize these new gender attitudes and behaviors and apply them in their own lives and relationships.

Results from the evaluation showed that becoming aware of inequalities, reflecting on the costs of rigid norms, and learning and practicing new skills (e.g., couple communication and joint decision-making) in a safe, non-judgmental peer environment, lead to changes across a range of health and relationship behaviors.

Community volunteers (local fathers) met with the same group of 12 men/couples on a weekly basis. The volunteers received a two-week training, material support, and refresher trainings from RWAMREC. Local nurses and police officers co-facilitated the sessions on pregnancy, family planning, and local laws, respectively. Sessions were conducted in local schools and administrative offices. RWAMREC staff monitored implementation of the group sessions and mentored the facilitators. Three intervention cycles, each with 570–576 couples, were implemented between March 2014 and July 2015. The Bandebereho RCT assessed the third cycle. The control group received no group intervention, though it did have access to community activities and campaigns related to the broader MenCare+ project through which the Bandebereho couples' groups were implemented. The intervention has been documented in greater detail in Doyle et al (2018).

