3.2. Study design

The study is designed as a six-year follow up of a randomized control trial with two arms: intervention and control. Couples were recruited into the intervention via the male partner in early 2015 and were later randomized to either the intervention or a control group. Due to the nature and structure of the intervention, randomization was done at the individual level. Randomization for the Bandebereho study took place in 2015, following the baseline survey (using the individual as the unit of randomization). The randomization was done by Laterite, an independent data collection firm, using a random number generator in Stata. Of the 1,199 men enrolled in the study, 575 men and their partners were randomized to the intervention (Bandebereho) group and 624 men and their partners were randomized to a control group, which received no intervention. Bandebereho community facilitators notified men of their assignment. All recruited men remained eligible for randomization to the intervention regardless of participation in baseline data collection.

The flow diagram of the Bandebereho RCT is included as Appendix 2.

Data were previously collected at three time points: baseline (February/March 2015); 9-month follow-up (November/December 2015); and 21-month follow-up (November/December 2016). Data were also collected from a subsample of respondents by phone, in August 2020, to better understand the impact of the Covid-19 virus on their lives. The proposed six-year follow-up will collect data in April and May 2021, approximately 72 months post-baseline. The study will seek to conduct in-person surveys with all couples enrolled in the original study (who are alive and traceable) and to conduct child assessments with a sub-sample of 800 children from 800 families.

Figure 1. Bandebereho RCT timeline

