Children	 a) Aged between 4 and 7 years; b) Biological child (of the male partner) living in the household of a man enrolled in the Bandebereho RCT; c) Whose parent has consented to the child's participation in the study d) Child provides assent to participate 	 a) If the child lives outside of the household (e.g. with other relatives, at an institution) b) If another child in the same family has been selected for assessment

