If the budget allows and anthropometric data (height and weight) are collected from children, the research team will also identify any children deemed at risk, i.e. in acute situations. An acute situation will be defined as a situation in which the respondent self-identifies or identifies his/her child as being in immediate danger, a child who meets initial screening criteria for severe acute malnutrition (sex-specific weight-for-height z-scores of less than -3 among children under 5) or severe thinness (sex-specific BMI-for-age z-scores less than -3 among children ages 5-7) based on WHO Growth Reference Data.

Laterite and the data collection team will take the following steps if a participant self-reports a risk of harm to self or others or if a parent identifies a risk of harm to their child:

- The enumerator will attempt to gather as much information as possible from the participant regarding the situation.
- The enumerator will fill out a risk of harm form with a description of the risk of harm case as reported by the participant.
- In the event of a life-threatening situation (for instance if a participant reports current suicidal thoughts or domestic abuse that puts the participant or their child's life in immediate danger):
 - \circ $\;$ the enumerator will reach out to RWAMREC staff for immediate referral.
 - RWAMREC staff (with experience working in the district where the respondent is located) will immediately contact the closest local leader to enable an immediate follow-up with the respondent to prevent and/or mitigate the risk of harm.
 RWAMREC and the local leader(s) will assess the situation and the most appropriate intervention (e.g., engagement of police, counselors) and intervene as quickly as possible.

- In the event of a non-life-threatening situation:
 - the enumerator will ask the participant if they agree to a referral to relevant services (e.g., police, counselling, etc.) prior to contacting RWAMREC staff.
 - RWAMREC staff (with experience working in the district where the respondent is located) will follow-up with the respondent to connect him/her to the relevant service in a safety and privacy.

Laterite will review and report risks of harm to Promundo, RWAMREC and RNEC within 48 hours.

All adult study participants, regardless of whether they disclose a risk of harm, will be offered a list of referral services at the end of the interview.

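### Children aged 4 to 7 in April and May 2021 are not only those born while the sessions ran or soon afterwards: the eligible birth window opens 10 to 22 months before the sessions began

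*Protocol*

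**What the plan says.** Section 4.1 describes those to be assessed as "children ages 4-7 (who would have been born in the period during or directly after the intervention". Section 3.4.1 is softer: "born around or shortly after the intervention, aged between 4 and 7 years". The criterion that decides eligibility, in Section 3.4.2, is age alone, "Aged between 4 and 7 years", together with conditions on parentage, household, consent and assent. It sets no limits on date of birth.

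The dates are elsewhere. Section 1.1 says that three cycles were "implemented between March 2014 and July 2015" and that the trial assessed the third. Section 3.2 puts baseline in February/March 2015, with randomisation after it, and says that the follow-up "will collect data in April and May 2021". Section 3.4.4 stratifies the child sample by arm and district. Where a family has several eligible children, "the child closest to age 6 would be selected".

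Section 4.2 names t-tests, chi-square tests and generalized estimating equations (GEE) with robust standard errors for the primary outcomes in general. It mentions no age term for the child scores.

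**The concern.** Objective (b) in Section 2 concerns children's development, and Table 4.1 lists child development among the primary outcomes. A reader of Section 4.1 will take the child result to describe children born during the sessions or soon after them. On the protocol's dates, the age range also admits children born well before the sessions and children conceived after randomisation.

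Two things follow.

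- **Interpretation.** The result would be attributed to a birth cohort narrower than the one eligible for sampling.
- **Analysis.** A child conceived after randomisation enters the sampling frame through an event that the intervention could have influenced. Sampling is not stratified by age, so nothing in the design balances age between arms. Scores for cognition and executive functioning are compared over three to four years of age, and a t-test leaves the variation due to age in the error term.

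**Working it through.** **Inputs**

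- Sessions for trial couples: from about March 2015 (after the February/March baseline, Section 3.2) to July 2015 (Section 1.1). Section 1.2 agrees: 21 months after baseline is 16 months after the intervention, and 21 − 16 = 5 months after baseline is July/August 2015. Section 1.3 also places the start six years before the follow-up.
- Assessment: taken as 1 May 2021, the middle of the planned period.
- Age range: 4 to 7. The upper limit is not defined. Two places point to completed years: the selection example in Section 3.4.4, "one child age 5 and another child age 7", and the screening text in Section 5.8.3, which separates under-fives from "BMI-for-age z-scores less than -3 among children ages 5-7".
- Gestation: nine months (an assumption, not in the protocol). Children born from about December 2015 were then conceived after randomisation.

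**Birth window** = assessment date minus the age limits.

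| | Completed years (4 to under 8) | Exact ages 4.0 to 7.0 |
|---|---|---|
| Eligible births | May 2013 to May 2017, 48 months | May 2014 to May 2017, 36 months |
| Before March 2015 | 22/48 = 46% | 10/36 = 28% |
| March to July 2015 | 5/48 = 10% | 5/36 = 14% |
| After July 2015 | 21/48 = 44% | 21/36 = 58% |
| Conceived after randomisation (part of the row above) | 17/48 = 35% | 17/36 = 47% |

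The description in Section 4.1 would require the first data row to be zero, and it is not under either reading of age. From 1 March 2015 to 1 May 2021 is 6 years 2 months, so any older eligible child was born before the sessions.

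**Sensitivity to dates.** Assessment was moved between 1 April and 31 May 2021, and the start between 15 February and 31 March 2015, with gestation of 266 days. In completed years, the share before the intervention is 43–50% and the share conceived after randomisation 32–39%. On exact ages they are 24–33% and 43–52%.

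**Wider reading of the intervention.** Counting all three cycles from March 2014 leaves 10/48 = 21% of the completed-years window before it (19–23% over the assessment dates), and none on exact ages.

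**Selection rule.** In completed years, the age-6 births run from May 2014 to April 2015, and 10 of those 12 months (83%) precede March 2015. On exact ages, the child closest to 6.0 was born near May 2015, which does fit. The rule removes the mismatch only on that reading, and only for families with a choice of child.

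**Precision.** Adjusting for age multiplies the standard error by √(1 − R²), where R² is the share of score variance that age explains. The protocol gives no value. If R² = 0.3, 1 − √0.7 = 16% reduction. If R² = 0.5, 1 − √0.5 = 29%. In sample-size terms this is 1/0.7 = 1.4 to 1/0.5 = 2.0 times the children.

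**The case against.** The strongest reply is that the sentence in Section 4.1 is a passing description. Eligibility rests on age, Section 3.4.1 is worded more loosely, and improving a couple's relationship and home can benefit children whenever they were born. Most of this stands. Mixed birth timing is not in itself a design fault, and more than half of the window does fit the description: 26/48 = 54% in completed years, 26/36 = 72% on exact ages. The description is still wrong for the rest, and it is what a reader will use to interpret objective (b).

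Four stronger readings are tempting, and the protocol does not support them.

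- *That 46% of the assessed children were born before the intervention.* The figures count calendar months. The mix among the 800 children depends on the original eligibility criteria (Appendix 1, not shown), birth patterns and the selection rule.
- *That the comparison is biased by fertility.* Section 1.2 reports an odds ratio of 1.53 for modern contraceptive use, but at 21 months, in November/December 2016. Children born by May 2017 were conceived by about August 2016, before that measurement. An effect of arm on births is plausible, but neither its size nor its direction is known.
- *That Section 4.2 plans only unadjusted t-tests for child scores.* It also lists GEE, assigns no test to a particular outcome, and covariates may be set in an analysis plan not seen here.
- *That children born or in utero at randomisation should be preferred at selection or form the main comparison.* Births before March 2015 would then make up 22/31 = 71% of the remaining window (10/19 = 53% on exact ages), further from the cohort that Section 4.1 describes.

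**Conclusion.** The concern holds in limited form. The protocol misdescribes who is eligible for the child assessments. Between 28% (exact ages) and 46% (completed years) of the eligible birth months precede the trial's own intervention. Between 35% (completed years) and 47% (exact ages) belong to children conceived after randomisation. This rests on a session period of about March to July 2015, assessment around 1 May 2021 and nine months' gestation. The mismatch survives both age readings and all the dates tried. It disappears only if the intervention is read as the whole 2013–15 project, or as all three cycles combined with exact ages, whereas Section 1.1 ties the trial to the third cycle.

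A difference between arms in child age or in which children exist is possible but not shown. The case for age adjustment does not depend on it: adjustment improves precision, by an amount that depends on an R² the protocol does not give.

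**What to change.** 1. In Section 4.1, give the actual range of birth dates. In Section 3.4.2, say whether age 7 means completed years or ends at the seventh birthday. Bring Sections 3.4.1, 3.4.2 and 4.1 into agreement.
2. In Section 4.2, state that child development scores are compared by the GEE or regression already planned, adjusted for age in months, sex and the sampling stratum (district), in place of a t-test. Date of birth is already to be confirmed from the vaccination card (Section 5.3).
3. Add a sensitivity analysis restricted to children born or in utero at randomisation, that is, born up to about December 2015. Their conception cannot have been affected by arm.

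Items 1 and 2 cost wording and the use of data already being collected. Item 3 costs precision: 31 of 48 birth months remain in completed years, or 19 of 36 on exact ages, so it should support the full-sample comparison and not replace it. The within-family selection rule can stay as it is.
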